### 10.5 Data Collection

We will use a standardized protocol to back-translate the relevant documents (sub-study information sheet, consent form and interview guide). Using the first draft version of the instruments, we will pilot test them for acceptability and clarity with three to five participants in each of the study languages. We will use feedback from the pilot test participants to revise the instruments and test them again with one person for each language, making final adjustments as needed. The interviewer will call the worker to: a)

review the sub-study information sheet, b) ensure the worker is eligible and still wants to be interviewed, and c) conduct the phone interview or schedule it for another time. The interviewer will use the semi-structured interview guide and record (with prior permission) the oral consent and interview. The telephonic interview will be conducted using the Exotel plug-in for SurveyCTO, which allows the form to make calls, the call would be recorded on the Exotel server, which would be only accessible to the GBL research team.

## 10.6 Data Analysis

The recorded interviews will be deidentified before being shared to an experienced bilingual transcriber who will transcribe the recording in the language used in the interview (Hindi, Kannada), and an accuracy check will be conducted by the GBL team member by comparing the audio and written versions of the interview. The bilingual translator will also produce an English-language version of each transcript, conferring with the interviewer to ensure accuracy.

The transcripts would be analysed using the Qualitative Content Analysis +Framework method. The analysis would be carried out in the following steps.

### 10.6.1 Prepare working transcripts.

**To start, we will create** working copies of each transcript, add line numbers (to help contextualise quotes during analysis), set aside less relevant statements and label each meaning unit (quote) with an anonymous source code (e.g. 'Int-6' = 6th participant from the Intervention Group).

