## 4.3 Trial design

PROSPER III is an investigator-masked, multi-centre mixed methods randomized controlled trial.

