## 4.5 Interventions

Eligible participants will be randomly assigned to Intervention or Control Groups (1:1). Intervention group participants will receive free reading glasses after undergoing a vision screening at the factories, which will mark the beginning of the assessment period. In addition to receiving free reading glasses, participants in the Intervention Group will be eligible for free replacement glasses in the event of loss or damage throughout the trial. Control group participants will receive free reading glasses at the end of the assessment period (18 months after the beginning of the assessment period). An interim analysis will be performed by the trial statistician. If the Trial Management Group (TSG) terminates the trial on the recommendation of the trial statistician, then Control Group participants will receive free reading glasses at trial closure. The trial will be investigator-masked, but not participant-masked, because the investigators do not feel provision of zero-power glasses to the control group is ethical. However, participants will have limited knowledge of the study hypothesis, limiting potential placebo effects.

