### **10. QUALITATIVE SUB-STUDY**

One of the hypotheses being tested in PROSPER III is providing glasses to correct presbyopia in sewing operators in India can reduce attrition. The RCT will collect data comparing the attrition rates of Intervention and Control group subjects; however, this will not explain why

sewing operators have left their jobs, and the role that vision plays in that decision. This qualitative sub-study will provide this additional information.

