### 10.6.2 Familiarisation

Analysis would be done by two or three researchers who will independently work with the transcripts and then confer until reaching consensus. The researchers will start by independently reading the whole document several times in order to become familiar with the information it contains. While reading the transcript from an interview, notes can be made on the margins which can be revisited later during the analysis.

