### 10.6.2 Produce analysis matrices

The researchers will create a blank table for each topic from the interview guide that they will populate with relevant quotes from transcripts (one quote per row). The tables will consist of five columns, one for the row number, another for the quote where we paste relevant statement or quote from the working transcript with the line number and source code; one column for the summary of the quote's meaning, the fourth column would be for the code which is to be developed from the meaning statements and finally the fifth column would be for the sub-code. The researchers will work independently on their own matrices and will then review the codes together and develop an agreed-upon list of codes.

pic.

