## **10.7 Outcomes**

- A rank-ordered list of reasons sew-ers have left Shahi or the textile industry
- A report on the role that poor near vision (uncorrected presbyopia) has on sew-ers' productivity, self-efficacy and job leaving
- Material for wider dissemination to academic audiences through presentations at conferences and publications in peer-reviewed journals

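### Interview quotes from leavers carry a source code that shows the treatment arm while they are being coded, in a trial described without exception as investigator-masked

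*SAP*

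**What the plan says.** Section 4.3 states: "PROSPER III is an investigator-masked, multi-centre mixed methods randomized controlled trial". Section 4.5 repeats the claim and limits it in one respect only: "The trial will be investigator-masked, but not participant-masked". Neither section defines who counts as an investigator, and neither makes an exception for the qualitative component.

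The sub-study in section 10 is meant to explain why "sewing operators have left their jobs, and the role that vision plays in that decision". Its outputs in section 10.7 are a ranked list of reasons for leaving and "A report on the role that poor near vision (uncorrected presbyopia) has on sew-ers' productivity, self-efficacy and job leaving".

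Working transcripts are prepared under section 10.6.1, where the researchers are to "label each meaning unit (quote) with an anonymous source code (e.g. 'Int-6' = 6th participant from the Intervention Group". The example code names the arm. Under Familiarisation, "Analysis would be done by two or three researchers who will independently work with the transcripts and then confer until reaching consensus". Under Produce analysis matrices (which is also numbered 10.6.2), they are to "paste relevant statement or quote from the working transcript with the line number and source code". In the same table, "the fourth column would be for the code which is to be developed from the meaning statements".

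**The concern.** Coding free text is a matter of judgement. A remark that the work had become too hard may or may not be coded as a vision problem. The trial's hypothesis is directional: section 4.2 expects better retention with glasses. A coder who sees a Control label beside such a remark may lean towards a vision reason, and may lean away from it beside an Intervention label. This can happen without intent.

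What is at stake is the credibility of the sub-study's account of vision and job leaving. Treatment status is one of the three sampling criteria in section 10.2, so comparing leavers by arm is a natural use of the data even though no such table is specified. If allocation was visible during coding, a reader of the report could not tell a real difference between arms from one that the coders' expectations created or enlarged.

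**Working it through.** No formula applies: the point depends on no sample size, event count or error rate. The check is whether the arm is visible when the judgements are made, and whether anything else in the SAP prevents that.

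1. **Labelling comes first.** The source code is attached in 10.6.1, when working transcripts are prepared. The same step sets aside statements thought less relevant, and nothing separates that selection from knowledge of the arm.
2. **Reading comes next.** Two or three researchers read the transcripts independently (10.6.2, Familiarisation).
3. **Coding follows with the label in view.** Each matrix row holds one quote with its line number and source code. The researcher fills in the meaning summary, the code and the sub-code in that same row (10.6.2, Produce analysis matrices).
4. **Outputs build on those codes.** They feed the codebook (10.6.3), the categories (10.6.4), the frequency tables (10.6.5) and the outputs in 10.7.
5. **De-identification does not help.** Section 10.6 de-identifies recordings before transcription, and 10.6.1 calls the code anonymous. Both can only refer to the person, because the example code itself gives the arm.
6. **The rigour measures do not mask coders.** Section 10.8 lists triangulation, peer debriefing, an audit trail, inter-coder reliability and reflexive journals. None of these withholds the arm. Independent coding, consensus and reliability checks reveal disagreement between coders. They cannot reveal an expectation shared by coders who all see the same label.
7. **The arm is not needed for coding.** Sampling by treatment status (10.2) requires only whoever draws up the call list to know it.

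Set against 4.3 and 4.5, the result is a masking statement that covers the whole mixed methods trial and a coding procedure that displays allocation, with no text reconciling the two.

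**Reach.** The primary outcome is employment status from the human resources database (4.6.1). The secondary outcome on reasons for leaving comes from supervisors and colleagues (4.6.2). Neither uses these transcripts.

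**The case against.** The strongest reply is that no breach of masking is shown. The SAP never says who is masked, and it does not place the coding researchers among the masked investigators. It also gives some study staff roles that reveal the arm: study personnel open assignments at enrolment (4.9), and staff observe spectacle wear each week (6). This stands. A reader might infer that people promised to be masked are unmasked by the label. The text supports only an unreconciled conflict between sections.

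A second reply is that the harm presumes a comparison the SAP does not plan. The frequency tables in 10.6.5 are arranged by topic and category, and the ranked list in 10.7 is not split by arm. Section 10.2 gives widening the range of responses as the reason for the strata. This also stands, so the by-arm consequence is conditional on such a comparison being made. The concern does not vanish without it, because codes assigned with the arm in view also feed the pooled account.

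Third, the design is descriptive and stays close to participants' words, so coders classify stated reasons. A reader might infer that the coders rule on whether vision caused each departure; the SAP does not give them that task. Classification still involves judgement when a statement is ambiguous.

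Fourth, a neutral code may achieve little, because workers know whether they received glasses and may say so. That limits the benefit, but it is no reason to reveal the arm where the worker does not. 'Int-6' is also only an example, yet it is the only convention that the SAP shows.

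**Conclusion.** The point holds as an avoidable risk of expectation bias, confined to the qualitative sub-study. Coders see allocation while classifying reasons for leaving, and the SAP neither masks them nor says that they are outside the masking claimed in 4.3 and 4.5. This rests on the example code being the convention actually used.

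The size cannot be quantified. A reader might be tempted to reason that 40 interviews give about 20 per arm, that three reclassified transcripts would then be 3/20 = 15 percentage points, and that this could reorder the ranked list. The SAP does not support that:

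- The number of ambiguous transcripts is unknown, and no expected distribution of reasons is given.
- Matrices hold quotes and the tables count codes, so the transcript is not the unit.
- The ranked list is not by arm; over all 40 interviews the same three would be 3/40 = 7.5 points.
- Section 10.2 allows 3–6 interviews in each of four cells per arm, so an arm could hold 4 × 3 = 12 to 4 × 6 = 24.

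No confirmatory inference is affected. The change is worth making because it is cheap and the plan's existing safeguards cannot detect this kind of bias.

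**What to change.** In 10.6.1, replace the example with an arm-neutral code such as 'P-06', carrying no information on arm, prescription strength or time of leaving. State that an existing team member who does not code holds the key, and that arm and strata are linked only after codes, categories and frequency counts are agreed. Carry the same code into the matrices. Add a sentence saying whether the qualitative coders are among the masked investigators. If the sponsor prefers coders who know the arm, the SAP should say so and state that they are separate from the masked investigators; that would settle the conflict but leave the bias risk.

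The cost is one change of labelling convention and the small task of keeping the key. Masking will be partial, since some workers will mention whether they received glasses, and the report should say so.

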### 10.6.2 Familiarisation

Analysis would be done by two or three researchers who will independently work with the transcripts and then confer until reaching consensus. The researchers will start by independently reading the whole document several times in order to become familiar with the information it contains. While reading the transcript from an interview, notes can be made on the margins which can be revisited later during the analysis.

### 10.6.2 Produce analysis matrices

The researchers will create a blank table for each topic from the interview guide that they will populate with relevant quotes from transcripts (one quote per row). The tables will consist of five columns, one for the row number, another for the quote where we paste relevant statement or quote from the working transcript with the line number and source code; one column for the summary of the quote's meaning, the fourth column would be for the code which is to be developed from the meaning statements and finally the fifth column would be for the sub-code. The researchers will work independently on their own matrices and will then review the codes together and develop an agreed-upon list of codes.

pic.

### **10.6.3 Create the Codebook**

A new word document labelled “Codebook” (the Analytical Framework) would be developed wherein the researcher would list each Code in alphabetical order along with any accompanying Sub-codes, then a brief definition of the Code/Sub-code and a sample quote that illustrates the Code/Sub-code. Every time the codebook is updated, the version number of each iteration of the document would be noted in the title page along with the date and source transcripts.

### **10.6.4 Creating Categories from codes**

A new document which is a second version of the matrices would be created. The researchers would identify Codes/Sub-codes that seem to “belong together” and group them into a category keeping the category names short and factual. Categories express the manifest (visible) content in the data, or what is visible and obvious, and answers the questions of “Who? What? When? or Where?” Since there can be overlap between codes and categories, sub-categories can be created to bridge codes and categories.

### **10.6.5 Interpreting the data**

The researchers would create a word document which contains the frequency table listing each category and codes for each topic. The frequency table will chart the data based on the Categories, listed in rank order from most to least frequently used, and the Codes/Subcodes they contain plus frequency counts. Illustrative quotes for each Category, particularly for the most frequently used Codes/Subcodes, will be provided under each frequency table along with a brief paragraph describing the meaning of the findings displayed in the frequency table.

An overall matrix would be created to chart the results as a single frequency table per Category along with an overall statement with supportive quotes based on the summary of findings from each transcript.

### **10.6.8 Write report**

The researchers will prepare a report on methods used to collect and analyse the data, as well as findings from both the qualitative content analysis (salience and relevance of categories within each topic) and thematic analysis.

## **10.7 Outcomes**

- A rank-ordered list of reasons sew-ers have left Shahi or the textile industry
- A report on the role that poor near vision (uncorrected presbyopia) has on sew-ers' productivity, self-efficacy and job leaving
- Material for wider dissemination to academic audiences through presentations at conferences and publications in peer-reviewed journals

## 10.8 Rigour

We will take several steps to ensure the qualitative sub-study is rigorous by following standard procedures aimed to fulfil the four criteria of excellence for qualitative research.

### 10.8.1 Credibility

Credibility (equivalent to internal validity) will be ensured through: a) prolonged and varied engagement with participants throughout the entire PROSPER III study; b) seeking referential adequacy by collecting documents and field notes that describe the study context; c) triangulation (the use of multiple data types and sources regarding worker attrition, and multiple investigators and perspectives); and d) producing high-quality findings through following a well-designed protocol for the sub-study, training the investigators, having an experienced qualitative researcher analyse field notes and analytic memos, and peer debriefing about the procedures and findings with qualitative experts not involved with the study.

### 10.8.2 Transferability

Transferability (equivalent to external validity or generalizability) will be enhanced by a) providing a rich description of methods, context, and findings; b) ensuring that sampling to data saturation was achieved; and c) data collection and analysis are done in a transparent way. This will allow others to decide if the methods and findings could be transferred to their setting or population (case-to-case generalization) or added to the literature on the study subject.

### 10.8.3 Dependability

Dependability (findings would be similar if the same cohort of participants, analysts and contexts existed) will be developed by maintaining a rich description of study methods and an audit trail or copy of all documents generated during the sub-study to allow others to inspect the methods used to reach study conclusions. Other methods include stepwise replication of the data analysis procedures through assessing coding accuracy and inter-coder reliability.

### 10.8.4 Confirmability

Confirmability (confidence that results can be corroborated by other researchers with similar participants, methods, and instruments) will be enhanced by triangulation (explained above), presenting information on the researchers and their positionality (e.g., experience with the research topic or study participants). Researchers will keep a 'reflexive journal' and share their experiences with the team at regular meetings, ensuring that their perspective does not overshadow the views and experiences of participants.

## 11. SAFETY DATA ANALYSIS

### 11.1 Serious adverse events

Serious adverse events will be listed by allocation as well as allocation received.

## **12. ADDITIONAL EXPLORATORY ANALYSIS**

Any analyses not specified in the analysis protocol will be exploratory in nature and a 2-sided significance level of 0.01 will be used with 99% confidence intervals.

## **13. DEVIATION FROM ANALYSIS DESCRIBED IN PROTOCOL**

None at present

